10.3. Informed Consent

Subjects who meet all of the inclusion criteria and none of the exclusion criteria and agree to participate in the NAVIGATE X4 Clinical Study must give written informed consent approved by the regional regulatory body and the investigational center's Institutional Review Board (IRB) or Ethics Committee (EC) prior to study participation and use of any investigational leads or testing/ data collection. The Informed Consent Form (ICF) must be in a language understandable to the subject and if needed, Boston Scientific will assist the center in obtaining a written consent translation. Translated consent forms must also have IRB/EC approval prior to their use. Subjects will be considered enrolled into the NAVIGATE X4 Clinical Study at the time the subject signs and dates the ICF.

10.4. Enrollment Visit

The data to be collected during enrollment into the NAVIGATE X4 Clinical Study includes patient demographic data, a physical assessment of the subject, including height and weight, vital signs, arrhythmia history, cardiac disease history, indications, and current cardiovascular medications. No study-specific procedures, device implant, or data collection may be conducted prior to consent.

Implant or attempted implant of the ACUITY X4 and/ or RELIANCE 4-FRONT Lead(s) must occur within 30 days of the subject signing informed consent.

10.4.1. Source Documentation Requirements

See Table 10 for required source documentation of the enrollment visit.

10.5. Implant Visit

The PG, investigational leads (ACUITY X4 and/ or RELIANCE 4-FRONT), and any other commercially available leads should be implanted and tested per standard procedures and in accordance with the Physician's Manuals for the associated PG and leads.

10.5.1. Pulse Generator Selection

Only a commercially available Boston Scientific Cardiac Resynchronization Therapy Defibrillator (CRT-D) with a quad header, or AUTOGEN X4 CRT-D (investigational in the US, see Section 4.7 for more detail) may be used in the NAVIGATE X4 Clinical Study*.

***Note:** in the event ACUITY X4 is attempted but not successfully implanted, BSC PGs (including ICDs) are allowed.

December 17, 2013
FINAL

Boston Scientific
NAVIGATE X4 Study Protocol
90874504 Version AB
Page 34 of 101

10.5.2. Atrial Lead Selection

Any commercially available atrial pace/sense lead may be used. Boston Scientific leads are preferred and recommended.

10.5.3. Right Ventricular Lead Selection

10.5.3.1. ██████████ NAVIGATE X4

Any commercially available Boston Scientific cardioversion/defibrillation lead may be used ██████████ NAVIGATE X4. BSC recommends the use of RELIANCE 4-FRONT. Documentation of RV lead choice will be collected ██████████ NAVIGATE X4.

10.5.3.2. ██████████ NAVIGATE X4

RELIANCE 4-FRONT is required in ██████████ NAVIGATE X4. If RELIANCE 4-FRONT is attempted, but not successfully implanted, the subject may still be a part of the study ██████████ ██████████ and a commercially available RV lead is acceptable. Boston Scientific RV leads are required.

10.5.3.3. RELIANCE 4-FRONT

When implanting RELIANCE 4-FRONT Active Fixation Leads, view the radiopaque markers under fluoroscopy to identify when the fixation helix is fully extended. Full extension is achieved when the radiopaque markers are joined and the fixation helix is extended outside the distal fluoroscopy markers (the expected number of rotations is 11 turns for 59 and 64 cm and 12 turns for 70 cm). Refer to Figure 4.

Figure 4: Fluoroscopic Views of the RELIANCE 4-FRONT Active Fixation Lead Helix

10.5.4. LV Lead Selection

Subjects enrolled in the NAVIGATE X4 study are required to be implanted and/ or attempted with an ACUITY X4 lead. In the event an ACUITY X4 lead is attempted, but not successfully implanted, only a market-released BSC unipolar or bipolar coronary venous lead is acceptable.

Note: In the event a BSC LV lead other than ACUITY X4 is implanted, data collected on these leads must follow that of sections 10.5.8, 10.5.11, 10.6.2, 10.7.2, and 10.8.1 (for RA and RV leads).

10.5.5. ACUITY X4 Left Ventricular Lead Selection

When selecting the appropriate ACUITY X4 lead for a subject, use the following guidelines.

December 17, 2013
FINAL

Boston Scientific
NAVIGATE X4 Study Protocol
90874504 Version AB
Page 35 of 101

Use venogram to identify a suitable target vein for lead implantation.

The three ACUIITY X4 lead tip configurations (Spiral S, Spiral L, and Straight) are available to provide appropriate choice for a variety of coronary veins. See below and Figure 5.

- ACUIITY X4 Spiral L is recommended when a target vein reaches the apical-third region of the heart, or mid-third of a severely dilated heart
- ACUIITY X4 Spiral S is recommended when a target vein reaches only the mid-third of the heart
- ACUIITY X4 Straight is recommended when a target vein is short, narrow, or tortuous

[figure not shown]

Figure 5: ACUIITY X4 Lead Selection

10.5.6. LV Lead Delivery Method Selection

The choice of the LV lead delivery system is left to physician discretion. Data regarding LV lead delivery method will be collected as a part of the NAVIGATE X4 Study database. Boston Scientific LV lead delivery systems are preferred and recommended.

10.5.7. Baseline ACUIITY X4 Lead Measurements with PSA

Documentation of PSA measurements for ACUIITY X4 leads will be required as described below for NAVIGATE X4 Study .

The required data to be collected from the implant procedure for all ACUIITY X4 includes PCT at 0.5 ms pulse width, sensed amplitude, and pacing impedance, measured with a pacing system analyzer (PSA) to verify adequate signals. Refer to Figure 6 below for a picture of the relationship between the terminal pin and ring contacts on the ACUIITY X4 quadripolar lead.

As stated in the ACUIITY X4 Physician’s Lead manual as a warning, only use the ACUIITY X4 Connector Tool for electrical connections to PSAs or similar monitors. Do not attach alligator

December 17, 2013
FINAL

Boston Scientific
NAVIGATE X4 Study Protocol
90874504 Version AB
Page 36 of 101

clips directly to the lead terminal or damage could occur. During ██████ NAVIGATE X4, it is required to perform a minimum of 6 threshold measurements as summarized in Table 8 and Figure 7 below. First, test 4 extended bipolar or 4 unipolar configurations (per physician discretion) to determine adequate electrode-myocardium contact. Test for the presence of extracardiac or phrenic nerve stimulation (PNS) for each electrode by pacing the lead at a high voltage output, using professional medical judgment to select the output voltage. If extracardiac stimulation is detected, measure stimulation PNS threshold. The four extended bipolar, or unipolar, measurements provide a relative threshold ranking among the electrodes which is associated to the proximity of each electrode to viable myocardium. Although thresholds may change, the relative ranking will be the same for bipolar measurements. Then select 2 bipolar measurements (one pair from E1 as the cathode (E2, E3, or E4 as the anode) and the other pair from E2, E3 or E4 as the cathode) to confirm the preferred distal and proximal pacing options. Use the best extended bipolar or unipolar ring electrode (from E2, E3, E4) as a cathode to any other ring electrode as an anode. Again, test for the presence of extracardiac or phrenic nerve stimulation for each electrode. If stimulation is detected, measure a PNS threshold. Refer to Table 8, Figure 6 and Figure 7 below.

The final test results of this testing must be printed from the PSA or documented on the Implant technical source documentation form and must be recorded on the Implant eCRF. BSC will also collect the PSA manufacturer and model number. Use the following figure to assist in connecting the AUCITY X4 lead to the PSA using the AUCITY X4 connector tool.

[figure not shown]

Figure 6: Relationship between the terminal pin and ring contacts with the distal tip electrodes E1 – E4

Table 8: AUCITY X4 PSA Testing Required during Implant

Pacing Configurations	# of Configurations and PNS Testing
Unipolar or extended bipolar measurements from each electrode, E1 through E4	4
Bipolar measurements between 2 of the electrodes: E1 → E2 E1 → E3 E1 → E4	2
Total configurations tested with PSA	6

December 17, 2013
FINAL

Boston Scientific
NAVIGATE X4 Study Protocol
90874504 Version AB
Page 37 of 101

[figure not shown]

Figure 7: ACUIY X4 Configurations to be Tested with PSA

10.5.8. Baseline PSA Measurements for RA and RV Leads

The optional data to be collected from the implant procedure for RA and RV leads, as well as ACUIY X4 includes pacing threshold, sensed amplitude, and pacing impedance, measured with a PSA to verify adequate signals before attaching the lead to the PG.

10.5.9. Loss of Capture and Threshold Definition

During the NAVIGATE X4 Study PCT measurements from the PG are collected from leads implanted in the LV, RA and RV in the standard manual fashion. At least 3 cardiac cycles at a given voltage level shall be obtained before stepping down to the next voltage level. A count of two non-capture beats is required at a given voltage level to declare a loss of capture (LOC) for any of these tests. The threshold is defined as one voltage level above the level where two non-captured beats are observed.

10.5.10. ACUIY X4 Lead Measurements with PG

Lead measurements, including pacing threshold (at 0.5 ms pulse width), sensed amplitude, and pacing impedance, are required to be collected using the CRT-D at implant for all implanted ACUIY X4 Leads. Pacing and sensing evaluation using the PG must be performed and the results recorded on the Implant eCRF. Lead measurements are required unless the testing is prohibited by a subject’s condition (subject has no intrinsic rhythm). The following measurements are to be taken utilizing the PG to ensure adequate sensing and pacing function of all ACUIY X4 Leads:

- Intrinsic amplitude (mV)*
- Pacing threshold (V, at 0.5 ms pulse width), details below in Table 9 and Figure 8
- Pacing lead impedance (Ω)*

December 17, 2013
FINAL

Boston Scientific
NAVIGATE X4 Study Protocol
90874504 Version AB
Page 38 of 101

*Note: the configuration used for sensed amplitude and lead impedance measurements is upon physician discretion. The nominal sensing configuration for ACUITY X4 is E1 →E2 (LV Tip 1 →LV Ring 2).

The pacing configurations that require PCT testing at the implant (through three-month follow up) are listed in Table 9 below and shown in Figure 8. If the investigator chooses to conduct multiple pacing threshold tests or on configurations not listed below on the ACUITY X4 Lead, only the final measurement and none of the initial measurements taken at 0.5 ms pulse width must be indicated on the eCRF.

Table 9: ACUITY X4 Pacing Configuration Required for PCT Testing at Implant, Pre-D and Three Months Post Implant

Pacing Configurations	# of Configurations tested
Unipolar or extended bipolar measurements from each electrode, E1 through E4	4
Bipolar between electrodes ^Δ : E1 →E2 E1 →E3 E1 →E4	3
Bipolar from the best electrode* on the lead to another electrode on the lead (excluding E1)	1
Total configurations tested	8

* Best electrode is the one that has the lowest threshold without phrenic nerve stimulation (PNS). In the event of a “tie” for best electrode, the investigator should use their medical judgment to select the best.

^Δ Nomenclature of electrodes on the lead (E1, E2, E3, E4) is an industry standard. The corresponding nomenclature on the BSC PRM is as follows:

- E1: LV Tip 1
- E2: LV Ring 2
- E3: LV Ring 3
- E4: LV Ring 4

Figure 8 below depicts the measurements required for the ACUITY X4 leads as described in the table above.

[figure not shown]

Figure 8: ACUITY X4 Lead Measurements Required at Implant, Pre-D and 3 Months

10.5.10.1. Phrenic Nerve Stimulation (PNS) Testing

Test for PNS in all aforementioned configurations and measure the PNS threshold if detected in the programmed configuration. The PNS threshold must be documented on the Implant technical source documentation form and must be recorded on the Implant eCRF.

10.5.11. RA and RV Lead Measurements with PG

Lead measurements, including pacing threshold, sensed amplitude, pacing impedance, and shock impedance are required at implant for all implanted RA (regardless of model) and RV Leads (RELIANCE 4-FRONT or commercially available RV lead). Pacing and sensing evaluation using the PG must be performed and the results recorded on the Implant eCRF. Lead measurements are required unless the testing is prohibited by a subject’s condition (subject has no intrinsic rhythm or is in atrial fibrillation). The following measurements are to be taken utilizing the PG to ensure adequate sensing and pacing function of all RA and RV Leads:

- Intrinsic amplitude (mV)
- Pacing threshold (V, at 0.5 ms pulse width; pulse width requirement for RELIANCE 4-FRONT leads only)

December 17, 2013
FINAL

Boston Scientific
NAVIGATE X4 Study Protocol
90874504 Version AB
Page 40 of 101

- Pacing impedance and
- Shock lead impedance (Ω)

If the investigator chooses to conduct multiple pacing threshold tests on the RA and/or RV Lead, only the final measurement and none of the initial measurements must be indicated on the eCRF.

10.5.12. Optional Ventricular Tachyarrhythmia Induction

Subjects are not required to undergo induction testing. Those subjects that undergo induction testing within 30 days of implant, per the discretion of the investigator, will be included in the analysis of the 4-FRONT Secondary Safety Endpoint and the 4-FRONT Secondary Effectiveness Endpoint 3. See Sections 11.2.4 and 11.2.8, respectively, for more information on these endpoints. The method of induction is per the physician's discretion but BSC strongly recommends the programmer/ PRM electrogram be run continuously during induction and delivery of therapy. VT/VF will be induced and the device allowed to sense and detect the arrhythmia (VT/VF Detection Time) and deliver programmed therapy (VT/VF Shock Conversion). The investigator shall allow the device to deliver at least one shock prior to external rescue, if appropriate. If multiple shock lead configurations (different shock vectors, polarities or lead positions) are tested, data from the final configuration must be used to document both detection time and shock conversion. VT/VF Detection Time is defined as the interval starting 250 ms after the last induction artifact (the time of the post induction ventricular refractory period) and ending at the "V-Episode Declared" marker. Programming of detection and duration should remain at nominal settings .

Steps for VT/VF induction:

1. Run programmer/PRM paper
2. Induce VT/VF
3. Allow device to sense and detect arrhythmia. Measure and record detection time.
4. Allow device to deliver therapy. Record conversion efficacy from final configuration.

If not done at implant, the physician may complete the optional VT/VF induction testing at pre-discharge or within 30 days of implant (at an additional follow up). Subjects may have additional VT/VF testing done if deemed appropriate.

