11.2.4. RELIANCE 4-FRONT Secondary Safety Endpoint

The purpose of this endpoint is to confirm that the RELIANCE 4-FRONT lead and its associated PG system have the ability to appropriately sense and detect VT/VF. Historically, this endpoint has been used to evaluate system performance; the lead is part of the system and therefore will be evaluated in this study. Subjects will not be required to undergo induction testing. Those subjects with a RELIANCE 4-FRONT lead that undergo induction testing within 30 days of implant, per the discretion of the investigator, will be included in the analysis and the time to detection of VT/VF will be measured.

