11.2.4.1. Hypotheses

The time it takes for the device to detect VT/VF will be compared to performance goal of 4.5 seconds, [redacted]

[redacted]

H₀: Induced mean VT/VF detection time ≥ 4.5 seconds

H_a: Induced mean VT/VF detection time < 4.5 seconds

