11.2.4.3. Statistical Methods

Data from all subjects with a RELIANCE 4-FRONT lead that have undergone an induction test within 30 days of implant will contribute to the analysis of this endpoint.

If multiple tests or multiple configurations are tested in the 30 day post-implant period, the last induction test in its final configuration will be used in the analysis. A one-sided one-sample t-test will be performed, using an alpha equal to [REDACTED]. If the t-test is deemed to be inappropriate based on the data, then a data transformation or a non-parametric test will be performed. If the p-value for the one-sided test is less than [REDACTED], the null hypothesis will be rejected.

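### VT/VF detection time has no value for an induced episode the device never declares, so the 4.5 s mean test in the RELIANCE 4-FRONT Secondary Safety Endpoint does not reflect detection failures

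*Protocol*

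**What the plan says.** Protocol 11.2.4 gives the purpose of the RELIANCE 4-FRONT Secondary Safety Endpoint: to confirm that the lead and pulse generator "have the ability to appropriately sense and detect VT/VF". Section 10.5.12 defines the measurement: "VT/VF Detection Time is defined as the interval starting 250 ms after the last induction artifact". The interval closes at the marker the device writes when it declares a ventricular episode.

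Section 11.2.4.1 sets the null as "Induced mean VT/VF detection time ≥ 4.5 seconds" and the alternative as "Induced mean VT/VF detection time < 4.5 seconds". Section 11.2.4.3 names a one-sided one-sample t-test, with this fallback: "If the t-test is deemed to be inappropriate based on the data, then a data transformation or a non-parametric test will be performed". It describes the contributing data as "Data from all subjects with a RELIANCE 4-FRONT lead that have undergone an induction test" within 30 days of implant, and the analysis-set table in 11.3.2 agrees. Where a subject is induced more than once, only the final induction in its final configuration is analysed.

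Neither 11.2.4 nor the SAP gives a penalty time, censoring rule, worst rank or detection-proportion criterion for an episode that was not declared. The redactions in 11.2.4.1 to 11.2.4.3 fall at the rationale for the goal, the sample-size inputs and alpha. The methods text is otherwise readable.

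**The concern.** The measure is the speed of detection given that detection happened. The stated purpose is the ability to detect. The two differ exactly in the subjects who matter most for safety: those whose induced arrhythmia the device did not recognise.

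The plan also conflicts with itself. It says every induced subject contributes, but the definition of the measurement leaves some of them without a value. Elsewhere missing information is taken seriously: tipping-point analyses are planned for the ACUITY X4 primary endpoints (11.1.3, 11.1.4.3, 11.1.5.3) and for both RELIANCE primary safety endpoints (11.2.1.3, 11.2.3). None is planned here, where a missing value may itself be the failure. The last-induction rule adds to this, because a non-detection followed by a successful retest is replaced by the retest.

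At stake is whether a favourable mean can be reported as evidence that the system detects VT/VF when the number of non-detections has not been shown.

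**Working it through.** **What can be reproduced.** Nothing. The expected mean, SD, N and alpha for this endpoint are redacted. The only document figures used are the 4.5 s goal (11.2.4.1) and, for Secondary Effectiveness Endpoint 3, the 93% goal with a one-sided 95% Clopper-Pearson lower limit (11.2.8.3). Everything else below is assumed: n = 200 inductions, detected mean 2.5 s, SD 1 s, one-sided alpha 5%, and a score of 20 or 30 s for an undetected episode.

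**1. Non-detections left without a value.** With 20 of 200 undetected, 180 remain. Z = (4.5 − 2.5) / (1/√180) = 26.8, so the null is rejected. At n = 100 with the same mean and SD, the mean stays at 2.50 s and the test still rejects with 50 of 100 undetected (p about 3 × 10⁻¹⁹). The size of the non-detection share makes no practical difference to the result.

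**2. Non-detections given a long score c.** The mean reaches 4.5 s when 2.5(1 − p) + c·p = 4.5, so p = 2.0 / (c − 2.5).
- c = 30: p = 2.0/27.5 = 7.3%.
- c = 20: p = 2.0/17.5 = 11.4%.

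These are the points where the mean equals the goal. The test stops rejecting earlier, because the long scores also inflate the SD. For k undetected of 200, the mean is [(200 − k)·2.5 + k·c]/200 and s² = [(199 − k)·1 + (200 − k)(2.5 − mean)² + k(c − mean)²]/199.
- c = 30, k = 10: mean 3.875 s, s = 6.09, t = −1.45, p = 0.074 (at k = 9, p = 0.032).
- c = 20, k = 17: mean 3.99 s, s = 4.99, t = −1.45, p = 0.074 (at k = 16, p = 0.041).

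Under these assumptions, about 10 of 200 (30 s) or 17 of 200 (20 s) turns a pass into a failure.

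**3. What Secondary Effectiveness Endpoint 3 would show.** Exact one-sided 95% lower limits for the success proportion:

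| Failures | Lower limit | Against 93% |
|---|---|---|
| 7 of 200 | 93.5% | pass |
| 8 of 200 | 92.9% | fail |
| 20 of 200 | 85.8% | fail |
| 19 of 400 | 93.1% | pass |

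Seven non-detections in 200 (3.5%) with no shock failures would pass both endpoints.

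**The case against.** The best case against the point has four parts.

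First, the plan is silent rather than wrong. A reader might infer that undetected subjects are excluded by rule, or that a failure to detect can never count against the lead. The documents do not support either reading. No passage excludes these subjects; 11.2.4.3 and 11.3.2 include all who were induced, and the non-parametric fallback could accommodate a worst rank. This stands as a limit on the wording. It does not fill the gap, because an interval with no end has no value until a score is assigned, and none is.

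Second, Secondary Effectiveness Endpoint 3 uses the same final induction and counts an externally rescued episode as a failure. Under the working assumptions it fails at 8 of 200, before the scored mean test would. So a substantial non-detection rate would not go unseen in the study. This also stands. But Endpoint 3 combines detection with shock failures, tolerates up to 7 in 200, and applies the same last-induction rule, so passing it cannot establish detection. (11.2.8.1 refers to the upper confidence limit and 11.2.8.3 to the lower; the figures here use the lower, the stricter of the two.) Undersensing is also a listed lead-related adverse event (19.3), but it reaches the complication-free rates only if it meets the definition in 19.3.1.

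Third, the endpoint is secondary, induction is optional, and study success rests on the primary endpoints (11.3.1). That limits the consequence.

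Fourth, replacing the hypothesis with a proportion detected within 4.5 s would need a new performance goal, and scoring at time of external rescue would measure the investigator's action rather than the device's. Both objections are accepted, and the fix avoids both changes.

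**Conclusion.** The point holds as a flaw in the stated measure of one secondary endpoint. As defined, the mean test describes how quickly the device detects when it does detect, and it cannot by itself support a claim about the ability to detect. It does not follow that the study is blind to non-detection, since Endpoint 3 and adverse event reporting can register it, or that the primary conclusions are affected.

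The size cannot be fixed from the documents. The break-even counts depend on the assumed n, mean, SD, alpha and penalty score, and the expected non-detection rate is unknown. What does not depend on those assumptions is that an undeclared episode supplies no value to the mean. The 3.5% tolerance in Endpoint 3 depends only on the assumed 200 inductions and the lower-limit rule in 11.2.8.3.

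**What to change.** Keep the test of the mean against 4.5 s, so that its link to the existing goal is preserved, and add the following to the SAP before the data are reviewed:

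1. An induced episode that the device does not declare counts as a detection failure for this endpoint.
2. The number and proportion of induced episodes detected are reported beside the mean, with an exact one-sided confidence limit. Non-detections on inductions later superseded by a retest are included and shown separately.
3. A supportive rank-based analysis against 4.5 s gives undetected episodes the worst rank. The detection claim is made only if it agrees with the test of the mean. A rank test concerns the centre of the distribution and would still agree when non-detections are few, so at low rates the reported proportion carries the information.

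The cost is SAP wording and one yes/no detection field per induction. No study procedure changes. The reported result may be slightly less favourable than the mean alone.
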